SOC	System Organ Class
TEAEs	Treatment Emergent AEs
TFLs	Tables Listings and Figures
uHCG	urinary β -human chorionic gonadotrophin
WHO	World Health Organization

1 INTRODUCTION

The purpose of this Statistical Analysis Plan (SAP) is to provide detailed descriptions of the statistical methods, data derivations and data displays for study protocol EVO100-311 Version 4.0 “Phase 3 double-blind placebo-controlled efficacy trial of EVO100 vaginal gel for the prevention of urogenital Chlamydia trachomatis (CT) and Neisseria gonorrhoeae (GC) infection (EVOGUARD)” dated 26MAY2021 for clinical study report (CSR) analysis. The table of contents and templates for the tables listings and figures (TFLs) will be produced in a separate document.

Any deviations from this SAP will be described and justified in the Clinical Study Report (CSR).

The preparation of this SAP has been based on International Conference on Harmonisation (ICH) E9.

All data analyses and generation of TFLs will be performed using SAS version 9.4 or higher.

2 STUDY OBJECTIVES

2.1 Primary Objective

- To evaluate the efficacy of EVO100 vaginal gel in the prevention of urogenital Chlamydia trachomatis (CT) and Neisseria gonorrhoeae (GC) infections.

2.2 Secondary Objective(s)

- To evaluate the safety of EVO100.

2.3 Exploratory Objective(s)

- To assess the impact of EVO100 vaginal gel on overall sexual satisfaction and overall product satisfaction over the course of the clinical study.
- To determine the impact of EVO100 vaginal gel use rate (subject adherence to instructed use) on the efficacy in the combined infections.
- To assess other subject satisfaction with EVO100 vaginal gel over the course of the clinical study.

3 STUDY DESIGN

3.1 General Study Design

At total of 1730 women, ages ≥ 18 , who had a documented urogenital CT or GC infection or an undocumented self-reported CT or GC infection with risk factors, at any time over the 17 weeks preceding the enrollment visit, or positive at screening visit will be enrolled. A high prevalence of CT infection has been observed in those who were treated for urogenital chlamydial infection during the preceding several months. The second infection may result from infection through an untreated partner or exposure through a new partner. By including only women who have had a CT or GC infection within the past 17 weeks, this study targets those at high risk for infection.

At screening, subjects will be tested for a current GC/CT infection by nucleic acid amplification test (NAAT) via vaginal swab. Those negative for current infection will be enrolled. Those who test positive for CT/GC infection at screening will receive standard of care treatment. To meet eligibility criteria, these subjects will not be enrolled until 3 to 4 weeks after screening (at least 21 days after treatment).

[figure not shown]
Eligible participants will be enrolled and randomized 1:1 (865 subjects per treatment arm) to either EVO100 Gel, 5g or HEC placebo 5 g supplied in a pre-filled, single-dose applicator. A baseline vaginal pH and a full gynecologic examination (including bimanual and speculum) will be obtained at enrollment.

Subjects are instructed to apply EVO100 or placebo gel immediately before or up to one hour prior to coitus for the duration of the 16-week intervention period. EVO100 or placebo is to be re-applied in the same manner for each occurrence of sexual intercourse. Subjects will keep an electronic diary (eDiary) to document sexual activity and product use.

Every 4 weeks (5 visits), all subjects will return to the clinic for repeat CT/GC NAAT (vaginal swab), urine pregnancy (urinary β -human chorionic gonadotrophin [uHCG]) testing, eDiary review, and return of unused investigational product. At Visits 2 to 4, subjects will be re-supplied with EVO100 or placebo gel. At Visit 5, subjects will return unused investigational product and continue to use their eDiaries but will not be resupplied with EVO100 or placebo gel.

Subjects will return for a follow-up visit 4 weeks after the intervention period or after their last dose of study medication. At this time, CT/GC NAAT (vaginal swab), pregnancy (uHCG) testing, gynecological exam, and eDiary review will be performed.

Figure 1 Schematic Flow of Study Design

Abbreviations: CT = *Chlamydia trachomatis*, GC = *Neisseria gonorrhoeae*, NAAT = nucleic acid amplification test

⁽¹⁾In the event a subject has CT or GC infection diagnosed at a local healthcare facility during the period between visits, the infection and treatment will be documented and every effort to obtain a medical record will be made.

Screening and Eligibility

Subjects who consent may be screened if they have a known case of CT or GC within 17 weeks of enrollment, or suspicion of current CT or GC infection (subsequently confirmed with NAAT test at Screening Visit). Subjects randomized within 35 days of initial screening do not need to be re-screened.

Intervention and Follow-up Period

The intervention period is defined as Visits 1 to 5. There will be one follow-up visit (Visit 6), 4 weeks after the last intervention visit or last dose of study product. These periods are outlined in the schedule of assessments (Table 2). The protocol-defined period of observation is 20 weeks. In the event a subject has CT or GC infection diagnosed at a local healthcare facility during the period between visits, the infection and treatment will be documented and every effort to obtain a medical record will be made. These subjects will be considered as failures.

Safety Follow-up After Protocol-defined Period of Observation

This period includes safety follow-up as required by Good Clinical Practice (GCP) and standard clinical study practice. Adverse events determined to be at least possibly related to the

investigational product continuing after the final study visit (Visit 6) will be followed until resolution or stable status as determined by the Investigator.

Study Conduct Strategies due to Coronavirus Disease -2019

Based on the US Food and Drug Administration (FDA) guidance, Coronavirus disease 2019 (COVID-19) strategies are planned for this study to ensure adherence to best practices for study conduct.

3.2 Randomization and Blinding

This is a Phase 3 placebo-controlled randomized study with 865 subjects per intervention arm, for a total of 1730 subjects. The 1730 subjects will be randomized using an Interactive Web Response System (IWRS) in a 1:1 fashion across the two intervention groups, EVO100 or placebo. Randomization will be stratified by prior infection documentation status (available/present versus unavailable/not present), and all documentation of this procedure and output will be saved with the IWRS vendor until the end of the study. Randomization will occur following enrollment and prior to issuance of investigational product to subjects.

Investigators and subjects in both intervention groups will remain blinded to their intervention assignment (EVO100 or placebo) over the entire duration of the study (double-blind). The Sponsor, E eofem, Inc., will prepare the investigational product as well as placebo and supply these products in ready-to-dispense status.

Any request from the Investigator for information about treatment dispensed to study subjects must be approved by the medical monitor.

If the code must be broken in the case of an emergency for management of a subject, the Investigator must provide a written request with record of the circumstances surrounding the event, including the purpose, date, and personnel involved. Emergency unblinding will be available by using the IWRS. An emergency treatment disclosure is a reportable event that must be reported to the Medical Monitor within 24 hours of the event.

Otherwise, blinding will not be broken until all subjects have completed the final study visit and the database has been locked and approved.

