4 STUDY ENDPOINTS

4.1 Primary Endpoint

- The primary efficacy endpoint is the proportion of subjects who are defined as study successes versus study failures among the intervention groups (EVO100 or placebo).
Estimand Framework
 - FDA Submission
 - Success is defined as subjects completing the trial to Visit 5 without any of the following: CT/GC infection, usage of prohibited antibiotics during the study, an invalid CT/GC test at Visit 5.
 - The mITT population will be used, and the Chi-Square test will be used to compare the failure rates in EVO100 and placebo.
 - EMA Submission
 - The parallel primary efficacy endpoints define success through Visit 5 as:
 - CT Infection Endpoint:
 - The proportion of subjects without a CT infection, CT prohibited antibiotics, or invalid Visit 5 CT test.
 - GC Infection Endpoint
 - The proportion of subjects without a GC infection, GC prohibited antibiotics, or invalid Visit 5 GC test.
 - The mITT population will be used and the Chi-Square test will be used to compare the failure rates in EVO100 and placebo.

Note: These two parallel primary endpoints enable efficacy to be assessed separately for CT and GC. In this way, if the study is successful for either CT or GC but not for both, an indication for prevention of just one of the two pathogens could still be granted. Both primary endpoints will be tested at the 0.05 significance level (with no adjustments for multiplicity of statistical testing).

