5 SAMPLE SIZE AND POWER

The primary analysis is a comparison between proportion of subjects who are defined study successes versus study failures (success defined as subjects completing the trial to Visit 5 without any CT or GC infection and no use of prohibited antibiotics; failures defined as subjects with CT infection, GC infection, use of prohibited antibiotics, or loss to follow-up) among the intervention groups (EVO100 or placebo).

It is assumed that the proportion of subjects who will have CT infection, GC infection, use of prohibited antibiotics, or loss to follow-up will be 30.5% for active treatment versus 37.5% for placebo group based on the Phase 2B/3 study (EVO003) with equal lost to follow-ups assumed in both intervention groups. Using a Chi-Square test for the primary endpoint, 821 analyzable subjects per treatment group (1642 subjects total) will yield approximately 85% power to detect a rate difference of 7% with a 2-sided 5% type I error rate. Given the assumption that 5% of subjects are found to be positive at enrollment, the total sample size planned for this study is 1730 subjects. With an assumed screen failure rate of approximately 27.8%, 2397 subjects are estimated to be needed for screening.

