8.6.1 Analysis Methods - Multiplicity

FDA Submission:

To control for multiple testing issues, a hierarchical testing strategy will be employed for exploratory endpoints that evaluate the efficacy of EVO100 vaginal gel in the prevention of urogenital CT and GC infection by assessing the proportions of subjects with:

- Overall sexual satisfaction using the FSFI overall sexual satisfaction question at Visit 5 and not having a CT or GC infection (Endpoint A), and
- Overall sexual satisfaction using the FSFI overall sexual satisfaction question at Visit 5 (Endpoint B).

If the primary endpoint is successful, then Endpoint A will be tested using a two-sided alpha=0.05. Endpoint B will be tested in succession if Endpoint A has a successful outcome.

EMA Submission:

For the EMA analysis, the primary endpoint can be either of the parallel primary endpoints for CT only and GC only. If either parallel primary endpoint is successful, then Endpoint A (same as above) will be tested using a two-sided alpha=0.05. Endpoint B (same as above) will be tested in succession if Endpoint A has a successful outcome.

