8.6.2 Analysis of Primary Endpoints

FDA Submission

For the primary analysis, the proportion of subjects who are defined study successes (i.e., have

all of the following through Visit 5: no CT/GC infection, no use of prohibited antibiotics, not lost to follow-up/otherwise discontinued, and no invalid CT/GC test at Visit 5) will be compared between the intervention groups (EVO100 or placebo) using a Chi-Square test. The primary efficacy analysis will be completed using the subjects deemed analyzable* from the mITT population.

*All subjects in the mITT population are deemed analyzable for the purpose of the primary endpoint analysis. Those subjects who are in ITT but not in mITT will be excluded from said analysis. The primary analysis will be performed using all subjects in the mITT population.

The primary statistical hypothesis being tested is that there is no difference in the proportion of subjects deemed study success in the EVO100 intervention group versus placebo. In statistical terms:

$$H_0: p_{EVO100} = p_{placebo}, H_A: p_{EVO100} \neq p_{placebo}$$

where, p_{EVO100} and $p_{placebo}$ denote the proportion of subjects deemed a study success while on EVO100 or placebo, respectively. Denominators for percentages are number of subjects in the mITT population in each intervention group. To test superiority over placebo, the percentage of study successes will be compared against placebo based using Chi-Square test. The estimated difference in proportions, 95% confidence interval, and p-value will be presented. A two-sided 5% type I error rate ($\alpha=0.05$) will be used. The Fisher's Exact test will be conducted in place of the Chi-Square test if necessary due to issues with the expected cell counts.

For the primary endpoint and exploratory analyses using CT/GC infection, any subject that does not have a known infection status through Visit 5 (i.e., at least through study day 105) (e.g., is deemed lost to follow-up) will be considered a failure. Likewise, any subject that uses prohibited antibiotics during the treatment period of the study regardless of CT/GC infection status will be considered a primary endpoint failure. Lastly, a patient having an invalid CT/GC test at Visit 5 will be considered a failure.

Secondary analyses of CT only and GC only endpoints will be performed as specified in the below EMA analysis section. See that section for more details.

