In addition, a sensitivity analysis will be provided for the primary endpoint. For the sensitivity analysis, the proportion of subjects who are defined as study successes will be irrespective of the use of prohibited antibiotics. Success will be defined as no CT/GC infection through Visit 5 (i.e., at least through study day 105). The statistical analysis described for the primary endpoint will be used for the secondary and sensitivity analyses.

A listing will be provided for CT/GC NAAT sample result.

EMA Analysis

For the parallel primary analyses, the proportion of subjects who are defined study successes will be compared between intervention groups (EVO100 or placebo) using a Chi-Square test. The primary efficacy will be completed using the subjects deemed analyzable* from the mITT population.

*All subjects in the mITT population are deemed analyzable for the purpose of the primary endpoint analysis. Those subjects who are in ITT but not in mITT will be excluded from said

analysis. The primary analysis will be performed using all subjects in the mITT population.

For the CT infection endpoint, success will be defined as having no CT infection, taking no CT prohibited medications, and no invalid CT test at Visit 5. For the GC infection endpoint, successes will be defined as having no GC infection, taking no GC prohibited medications, and no invalid GC test at Visit 5.

The primary statistical hypothesis being tested is that there is no difference in the proportion of subjects deemed study success in the EVO100 intervention group versus placebo. In statistical terms:

$$H0: pEVO100 = pplacebo, HA: pEVO100 \neq pplacebo$$

where, pEVO100 and pplacebo denote the proportion of subjects deemed a study success while on EVO100 or placebo, respectively. Denominators for percentages are number of subjects in the mITT population in each intervention group. To test superiority over placebo, the percentage of study successes will be compared against placebo based using Chi-Square test. The estimated difference in proportions, 95% confidence interval, and p-value will be presented. A two-sided 5% type I error rate ($\alpha=0.05$) will be used. The Fisher's Exact test will be conducted in place of the Chi-Square test if necessary due to issues with the expected cell counts.

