8.6.3 Analysis of Exploratory Endpoints

The following summary and analysis will be provided for the exploratory endpoint using mITT population:

Patient-reported outcomes measures for this study are to evaluate the efficacy of EVO100 vaginal gel in the prevention of urogenital CT and GC infection by assessing the following proportions of subjects:

- With overall sexual satisfaction using the FFSI overall sexual satisfaction question at Visit 5 (i.e., at least through study day 105) and not having a CT or GC infection using FDA primary endpoint rules.
- With overall sexual satisfaction using the FFSI overall sexual satisfaction question at Visit 5 (i.e., at least through study day 105).
- Reporting overall product satisfaction at Visit 5 (i.e., at least through study day 105).
- A subset analysis of the primary endpoint (FDA rules) looking at results based on prior infection documentation will be performed.

Above endpoints will be compared against placebo based on Chi-Square test. The estimated difference in proportions, 95% confidence interval, and p-value will be presented. A two-sided 5% type I error rate ($\alpha=0.05$) will be used. The Fisher's Exact test will be conducted in place of the Chi-Square test if necessary due to issues with the expected cell counts.

From the FFSI questionnaire, question (#16) "over the past 4 weeks, how satisfied have you been with your overall sexual life?" will be considered for sexual satisfaction. The question from product satisfaction questionnaire "How satisfied are you with the study product?" will be used

to assess the overall product satisfaction. Responses will be categorized as satisfied (i.e., combined responses of very satisfied, moderately satisfied, about equally satisfied and dissatisfied) and dissatisfied (i.e., combined response of moderately & very dissatisfied) for the comparison.

Additional exploratory endpoints are:

- Compliance with EVO100 vaginal gel usage versus placebo usage during study (rate of product use adherence and placebo) will be summarised descriptively (see [section 8.5](#) for more details).
- The proportion of subjects who are defined success versus failure (FDA primary endpoint) will be summarized using the below adherence categories by treatment groups. The estimated difference in proportions, 95% confidence interval, and p-value will be presented.

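### Randomisation is stratified by prior infection documentation, but the efficacy tests ignore the stratum; a stratified test would be a small gain at no material cost.

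*SAP*

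**What the plan says.** SAP 3.2 sets 1:1 allocation through the IWRS and states: "Randomization will be stratified by prior infection documentation status (available/present versus unavailable/not present".

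The tests that follow do not use that factor:

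- **FDA and EMA primaries (SAP 4.1).** Under each submission, "the Chi-Square test will be used to compare the failure rates in EVO100 and placebo".
- **FDA primary (SAP 8.6.2).** Success proportions "will be compared between the intervention groups (EVO100 or placebo) using a Chi-Square test", reported with the estimated difference and a 95% confidence interval. Fisher's exact test is the fallback.
- **EMA parallel primaries for CT and GC (SAP 8.6.2).** Success proportions "will be compared between intervention groups (EVO100 or placebo) using a Chi-Square test", with the same estimate and fallback.
- **Sensitivity analysis and CT-only and GC-only secondaries (SAP 8.6.2).** "The statistical analysis described for the primary endpoint will be used for the secondary and sensitivity analyses".
- **Endpoints A and B.** SAP 8.6.1 places them in the hierarchy: "If the primary endpoint is successful, then Endpoint A will be tested using a two-sided alpha=0.05", with B tested if A succeeds. SAP 8.6.3 gives the method: "Above endpoints will be compared against placebo based on Chi-Square test".

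SAP 5 is built on the same unstratified test: "Using a Chi-Square test for the primary endpoint, 821 analyzable subjects per treatment group" are said to give about 85% power.

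Documentation status reappears only as an exploratory subset of the FDA primary (SAP 8.6.3, Section 9 item 6, Table 14.2.1.6). No stratified test, stratified interval or covariate adjustment is named. The documents do not say why the factor was chosen or whether it predicts outcome.

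**The concern.** When randomisation is stratified on a factor that predicts outcome, the arms are balanced on that factor, and the true variance of the crude difference is smaller than under unstratified allocation. The ordinary chi-square estimates its standard error as if no balancing had been done. It is then slightly conservative and its interval slightly too wide, so some of the benefit of stratifying is left unused.

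It is plausible, though not shown, that the strata differ in risk, because they enter by different rules. In the Protocol synopsis, inclusion criterion 1, subjects with a medical record need at least one further risk factor; those without need at least two, plus self-reported infection. The direction is not obvious: undocumented subjects may carry more risk factors, or some may not have had the infection they report.

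At stake is a little power and precision. Type I error is not inflated and the sample size is not wrong for the planned test.

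**Working it through.** **Inputs from the documents.** SAP 5: n = 821 analyzable per arm; failure pE = 0.305 and pP = 0.375; two-sided alpha 0.05. Mean failure rate pbar = (0.305 + 0.375)/2 = 0.34; difference 0.07.

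**Assumed, because the documents are silent.** Stratum shares w and 1 − w; failure risk differing by d between strata; the same 7-point treatment difference in both strata; arms balanced within strata.

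**Step 1: reproduce the SAP's figure.**

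- SE_pool = √(2·pbar·(1 − pbar)/n) = √(0.4488/821) = 0.02338
- SE_true with d = 0: √((0.305·0.695 + 0.375·0.625)/821) = √(0.44635/821) = 0.02332
- Power = Φ((0.07 − 1.96·0.02338)/0.02332) = Φ(1.037) = 85.0%

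The stated 85% is reproduced.

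**Step 2: add the stratum.** Balancing on a two-level factor removes 2·w·(1 − w)·d² from each numerator under the square root:

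- SE_str0 = √((0.4488 − 2w(1 − w)d²)/821), the null standard error of the stratified test
- SE_true = √((0.44635 − 2w(1 − w)d²)/821), the actual standard error of the difference
- Crude power = Φ((0.07 − 1.96·SE_pool)/SE_true)
- Stratified power = Φ((0.07 − 1.96·SE_str0)/SE_true)
- Crude type I error = 2Φ(−1.96·SE_pool/SE_str0)
- Stratified 95% half-width = 1.96·SE_true

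*Worked case, 50/50 split and d = 0.20.* The amount removed is 2·0.25·0.04 = 0.02.

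- SE_str0 = √(0.4288/821) = 0.02285; SE_true = √(0.42635/821) = 0.02279
- Crude power = Φ(1.061) = 85.6%; stratified power = Φ(1.106) = 86.6%
- Crude type I error = 2Φ(−2.005) = 0.045
- Half-width = 1.96·0.02279 = 4.47 points, against 1.96·0.02332 = 4.57 for the crude interval

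**Step 3: the range.**

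| Split | Gap d | Crude power | Stratified power | Gain (points) | Crude type I | Stratified half-width (points) |
|---|---|---|---|---|---|---|
| any | 0 | 85.0% | 85.0% | 0 | 0.050 | 4.57 |
| 90/10 | 10 points | 85.1% | 85.2% | 0.1 | 0.050 | 4.56 |
| 70/30 | 5 points | 85.0% | 85.1% | 0.05 | 0.050 | 4.57 |
| 70/30 | 10 points | 85.1% | 85.3% | 0.2 | 0.049 | 4.55 |
| 70/30 | 15 points | 85.3% | 85.8% | 0.5 | 0.048 | 4.52 |
| 50/50 | 15 points | 85.3% | 85.9% | 0.6 | 0.047 | 4.51 |
| 50/50 | 20 points | 85.6% | 86.6% | 1.0 | 0.045 | 4.47 |

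In sample-size terms, the last row equals 821 × (0.4488/0.4288 − 1) ≈ 38 subjects per arm. At an extreme 50/50 split and 30-point gap, the gain is 2.2 points (86.3% to 88.5%).

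**Step 4: simulation.** With 1,000,000 trials per case, chi-square versus Cochran-Mantel-Haenszel power was 85.2% vs 85.3% (70/30, 10 points), 85.3% vs 85.7% (70/30, 15 points), 85.4% vs 85.9% (50/50, 15 points) and 85.6% vs 86.6% (50/50, 20 points). Type I error was 4.9%, 4.8%, 4.7% and 4.5% for the crude test and 5.0% throughout for the stratified one. In a separate simulation with no gap (400,000 trials per case), the two tests differed by no more than 0.02 points of power.

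The documents give no rates for CT-only, GC-only or Endpoints A and B, so no gain is computed for them.

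**The case against.** The strongest reply is that nothing is broken. The chi-square is pre-specified, holds its type I error at or below 5%, and is the test the trial was powered on, so design and analysis agree. Choosing between two valid tests is a preference. That stands, and it fixes the priority as low.

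The gain is also hypothetical. The Protocol opens the undocumented route only after three failed attempts to obtain records, which suggests a minority stratum. The FDA endpoint also counts loss to follow-up, prohibited antibiotics and invalid Visit 5 tests as failures, and nothing says documentation status predicts those. This stands too: the lower rows of the gain are more likely than the 1.0-point row.

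Third, the conservatism depends on close balance within strata, and SAP 3.2 mentions no blocks. That is a fair condition to state, but it does not remove the gain. If allocation within strata were by simple 1:1 chance (50/50, 20 points), simulation puts crude type I error at 5.0% and power at 84.9% crude versus about 86.4% stratified, a gain of about 1.5 points.

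Last, SAP 8.6.3 also uses chi-square tests for product satisfaction and for the failure components, and Section 9 adds an age subgroup. These can remain unstratified without making the change below unsound, although the components would then be tested differently from the composite.

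**Conclusion.** The mismatch between stratified randomisation and unstratified analysis is real and covers every test listed above. It is a minor, optional improvement. For gaps of up to 20 points between strata, the gain for the FDA primary runs from nil to about 1 point of power, and the interval narrows by at most 0.1 points (4.57 to 4.47). These figures rest on assumed stratum shares and gaps, a constant 7-point treatment difference and balance within strata. Confidence is high on the mismatch and low on the size of the gain, which may be zero.

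**What to change.** Before unblinding, amend the SAP as follows.

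- **SAP 4.1 and 8.6.2** (FDA primary, both EMA primaries, sensitivity analysis, CT-only and GC-only secondaries) **and 8.6.3 for Endpoints A and B:** use a Cochran-Mantel-Haenszel test stratified by documentation status as randomised in the IWRS. In 8.6.3, separate A and B from the sentence that now also covers product satisfaction and the subset analysis.
- **Estimate:** report the Mantel-Haenszel risk difference with a 95% interval using the Sato variance.
- **Sparse cells:** replace Fisher's exact test with an exact conditional stratified test.
- **Retain** the crude chi-square as a sensitivity analysis, and leave the subset analysis by documentation status unstratified.
- **Section 9:** add one line recording the change.

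The cost is text edits and modest programming. No subjects, visits or data are added: the stratum is held in the IWRS, and documentation status is already needed for Table 14.2.1.6.
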